10.1 Definition of adverse events and reporting requirements

10.1.1 Adverse events

An adverse event (AE) is any untoward medical occurrence (e.g., any unfavorable and unintended sign [including abnormal laboratory findings], symptom or disease) in a subject or clinical investigation subject after providing written informed consent for participation in the study. Therefore, an AE may or may not be temporally or causally associated with the use of a medicinal (investigational) product.

The investigator has the responsibility for managing the safety of individual subject and identifying adverse events.

Novartis qualified medical personnel will be readily available to advise on trial related medical questions or problems.

The occurrence of adverse events must be sought by non-directive questioning of the subject at each visit during the study. Adverse events also may be detected when they are volunteered by the subject during or between visits or through physical examination findings, laboratory test findings, or other assessments.

Adverse events must be recorded in the Adverse Events CRF under the signs, symptoms or diagnosis associated with them, accompanied by the following information (as far as possible) (if the event is serious refer to [Section 10.1.2](#)):

1. the severity grade
 - mild: usually transient in nature and generally not interfering with normal activities
 - moderate: sufficiently discomforting to interfere with normal activities
 - severe: prevents normal activities
2. its relationship to the study treatment. If the event is due to lack of efficacy or progression of underlying illness (i.e., progression of the study indication) the assessment of causality will usually be 'Not suspected'. The rationale for this guidance is that the symptoms of a lack of efficacy or progression of underlying illness are not caused by the trial drug, they happen in spite of its administration and/or both lack of efficacy and progression of underlying disease can only be evaluated meaningfully by an analysis of cohorts, not on a single subject
3. its duration (start and end dates) or if the event is ongoing, an outcome of not recovered/not resolved must be reported.
4. whether it constitutes a SAE (see [Section 10.1.2](#) for definition of SAE) and which seriousness criteria have been met
5. action taken regarding with the study treatment.

All adverse events must be treated appropriately. Treatment may include one or more of the following:

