- Dose not changed
 - Dose reduced/increased
 - Drug interrupted/withdrawn
6. its outcome:
 - a. not recovered/not resolved;
 - b. recovered/resolved;
 - c. recovering/resolving,
 - d. recovered/resolved with sequelae;
 - e. fatal, or
 - f. unknown.

Conditions that were already present at the time of informed consent should be recorded in medical history of the subject.

Adverse events (including lab abnormalities that constitute AEs) should be described using a diagnosis whenever possible, rather than individual underlying signs and symptoms.

Adverse event monitoring should be continued until the EoS visit.

Once an adverse event is detected, it must be followed until its resolution or until it is judged to be permanent (e.g., continuing at the end of the study), and assessment must be made at each visit (or more frequently, if necessary) of any changes in severity, the suspected relationship to the interventions required to treat it, and the outcome.

Information about adverse drug reactions for the investigational drug can be found in the Investigator Brochures (IBs).

Any new information regarding the safety profile of the medicinal product that is identified between IB updates will be communicated as appropriate, for example, via an Investigator Notification. New information might require an update to the informed consent and has then to be discussed with the subject.

Abnormal laboratory values or test results constitute adverse events only if they fulfill at least one of the following criteria:

- they induce clinical signs or symptoms
- they are considered clinically significant
- they require therapy

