12.5.2 Safety endpoints

For all safety analyses, the safety set will be used. All listings and tables will be presented by period and treatment group.

Safety summaries (tables, figures) include only data from the on-treatment period with the exception of baseline data which will also be summarized where appropriate (e.g., change from baseline summaries). In addition, a separate summary for death including on treatment and post treatment deaths will be provided. In particular, summary tables for adverse events (AEs) will summarize only on-treatment events, with a start date during the on-treatment period (*treatment-emergent* AEs).

The on-treatment period lasts from the date of first administration of study treatment until end of study (EoS).

Adverse events

All information obtained on adverse events will be displayed by treatment group and subject.

The number (and percentage) of subjects with treatment emergent adverse events (events started after the first dose of study medication or events present prior to start of double-blind treatment but increased in severity based on preferred term) will be summarized in the following ways:

1. by treatment group, primary system organ class and preferred term.
2. by treatment group, primary system organ class, preferred term and maximum severity.

Separate summaries will be provided for study medication related adverse events, death, serious adverse events, other significant adverse events leading to discontinuation and adverse events leading to dose adjustment.

The number (and proportion) of subjects with adverse events of special interest will be summarized by treatment group. A subject with multiple adverse events within a primary system organ class is only counted once towards the total of the primary system organ class.

Vital signs

All vital signs data will be listed by treatment group, subject, and visit and if ranges are available, abnormalities will be flagged. Summary statistics (e.g., change from baseline and shift tables) will be provided by treatment group and visit.

12-lead ECG

All ECG data will be listed by treatment group, subject and visit, abnormalities will be flagged. Summary statistics will be provided by treatment group and visit.

1. PR, QRS, QT, QTcF, and RR intervals will be obtained from 12-lead ECGs for each subject during the study. ECG data will be read and interpreted (/locally).

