The number and percentage of patients with clinically notable laboratory results after baseline will be presented.

Adverse events

All information obtained on adverse events will be displayed by treatment and participant.

The number and percentage of patients with adverse events will be tabulated by body system and preferred term with a breakdown by period and treatment. A patient with multiple adverse events within a body system is only counted once towards the total of this body system and treatment. Separate tables and listings will be presented indicating event severity and study drug relationship.

The on-treatment/ treatment emergent period lasts from date of first administration of study treatment until end of study (EoS). Summary tables for adverse events (AEs) will summarize only on-treatment events, with a start date during the on-treatment period (treatment emergent AEs).

For the legal requirements of ClinicalTrials.gov and EudraCT, two required tables on <on-treatment/treatment emergent> adverse events which are not serious adverse events with an incidence greater than 5% and on <on-treatment/treatment emergent> serious adverse events and SAE suspected to be related to study treatment will be provided by system organ class and preferred term on the safety set population.

If for a same patient, several consecutive AEs (irrespective of study treatment causality, seriousness and severity) occurred with the same SOC and PT:

- a single occurrence will be counted if there is ≤ 1 day gap between the end date of the preceding AE and the start date of the consecutive AE
- more than one occurrence will be counted if there is > 1 day gap between the end date of the preceding AE and the start date of the consecutive AE.

For occurrence, the presence of at least one SAE / SAE suspected to be related to study treatment / non-SAE has to be checked in a block e.g., among AE's in a ≤ 1 day gap block, if at least one SAE is occurring, then one occurrence is calculated for that SAE.

The number of deaths resulting from SAEs suspected to be related to study treatment and SAEs irrespective of study treatment relationship will be provided by SOC and PT.

Injection-related Reactions

Injection-related reactions will be summarized by type of injection reaction (overall, local and systemic), by grading, and by visit. Injection-related reaction events will be listed by treatment, patient and visit/time.

Other safety evaluations

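### Protocol 12.5.2 gives two conflicting rules for treatment-emergent adverse events, and SAP 8.2 keeps only the one that leaves out pre-dose events that worsen after dosing

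*SAP*

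**What the plan says.** **SAP 8.2, Adverse events.** The treatment-emergent period runs from first administration of study treatment to end of study. The SAP states that the AE summary tables will "summarize only on-treatment events, with a start date during the on-treatment period". It has no clause for an event that is already present at first dose and then gets worse. Listings are not restricted in this way: "All information obtained on adverse events will be displayed by treatment and participant".

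**Protocol 12.5.2.** An early paragraph gives the same start-date rule: "summary tables for adverse events (AEs) will summarize only on-treatment events, with a start date during the on-treatment period". Under the Adverse events subheading, the section then describes treatment-emergent events as those starting after first dose, or "events present prior to start of double-blind treatment but increased in severity based on preferred term". That second description is attached to two tables: by system organ class and preferred term, and the same with maximum severity.

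**Protocol 10.1.1.** An AE is an untoward occurrence "after providing written informed consent for participation in the study", so an AE can be on record before first dose. Conditions already present at consent go to medical history. Once an AE is detected it is followed to resolution, and "assessment must be made at each visit (or more frequently, if necessary) of any changes in severity".

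**The concern.** Two rules in one protocol section give different answers for the same event, and the SAP, which should settle the matter, repeats one of them without comment. The events on which they differ matter for safety: something was present before treatment and became more severe on treatment. If such an event stays in one record with its pre-dose start date, the start-date rule removes it from the summary tables, including the maximum-severity table, where a worsening would be most informative. A programmer following the SAP and a reader relying on the protocol's worsening clause would then disagree about what the tables contain.

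**Working it through.** No figure in the plan depends on this point, so the check is a comparison of text.

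**Step 1: apply each rule to the possible cases.**

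| AE history | Start-date rule (SAP 8.2; early paragraph of protocol 12.5.2) | Worsening definition (later in protocol 12.5.2) |
|---|---|---|
| Starts after first dose | Counted | Counted |
| Starts between consent and first dose, never worsens | Not counted | Not counted |
| Starts between consent and first dose, worsens after dosing, one record | **Not counted** | **Counted** |
| As above, but the worsening is a new record dated after first dose | Counted | Counted |

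The rules differ only in the third row.

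**Step 2: can the third row occur?** AEs are recorded from consent (protocol 10.1.1), and the screening period is 28 days (protocol section 3; SAP 1.4). A pre-dose AE is therefore possible. The group is narrow: onset must fall in that window and the worsening must come after dosing.

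**Step 3: one record or two?** The documents do not decide this.

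- For one record: protocol 10.1.1 follows an AE to resolution and assesses severity changes along the way, and protocol 10.1.3 reports progression of an SAE as follow-up to the original episode.
- For two records: the SAE definition in protocol 10.1.2 treats worsening of a pre-existing condition as an event; protocol 12.5.2 judges the increase at preferred-term level; and the SAP 8.2 rule for consecutive AEs with the same term, whatever their severity, allows for back-to-back records.

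No section says which start date applies after a worsening.

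**Step 4: size.** The number of such AEs is not given and cannot be derived. Only the weight of one patient can be stated. With 30 per arm (protocol 12.8.1):

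- 1/30 = 3.3%
- 2/30 = 6.7%

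SAP 8.2 plans a registry table of non-serious AEs with incidence above 5%. In an arm of 30, a preferred term seen in two patients passes that threshold and one seen in a single patient does not. Leaving out one patient could therefore decide whether a term is listed. This shows sensitivity and does not estimate how often it would happen.

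**Step 5: direction.** Within any arm, the start-date rule can only give the same count or a lower one. Between arms, it drops such events from active and placebo alike. The comparison shifts only if post-dose worsening differs between arms, and the documents give no information on that.

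**The case against.** The strongest reply is that the loss may never happen. If sites open a new record when severity increases, the start-date rule already counts the event. Step 3 shows real textual support for that practice, and nothing in protocol 10.1.1 says that a worsening keeps the original start date. This stands: the omission is conditional on a convention that neither document states. It does not remove the contradiction, because the plan should not depend on an unstated convention.

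Second, the SAP follows a sentence that is in the protocol, so it has not simply departed from the protocol. This also stands. The inconsistency lies first inside protocol 12.5.2.

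Third, the study is non-confirmatory and its safety tables are descriptive. That limits the consequence, but the remedy is also small.

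A reader might infer more than the documents support:

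- **That these events vanish from all AE output.** The rule covers summary tables; the listings show all AE information. The SAP does not expressly say whether the rule reaches the table of deaths from SAEs.
- **That the rule makes VAY736 or CFZ533 look safer than placebo comparisons would otherwise show.** It applies to both arms, and no difference in worsening is documented.
- **That several patients per arm are affected, giving understatements of up to 10 points.** No source supports any count.
- **That crediting to placebo an event that starts on placebo and worsens after the Week 29 switch breaches the protocol.** The worsening clause refers only to events present before double-blind treatment, and neither document states how such an event is assigned to a period. The SAP places derivations in a separate programming specification that is not part of these documents.

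**Conclusion.** The point holds as a definitional conflict. Protocol 12.5.2 states two incompatible rules for the same AE summary tables, and SAP 8.2 adopts the narrower one. An AE that starts between consent and first dose, worsens afterwards and remains a single record is left out of those tables, although the protocol's worsening clause would include it. This rests on one assumption that the documents do not settle, namely that a worsening is not entered as a new dated record. The affected group is narrow, its size is unknown, and no bias between arms is shown. It is worth correcting because the change is cheap and can only add relevant events.

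**What to change.** 1. Use one treatment-emergent definition in protocol 12.5.2 and SAP 8.2: an AE that starts on or after first dose, or one present before first dose that increases in severity afterwards, judged by preferred term.
2. Remove the start-date-only sentence from both places.
3. State how a severity increase is recorded and dated: as a new record, or as a dated change within the existing one.
4. As an added proposal that the protocol does not now require, state how the by-period tables assign an AE that starts in the blinded period and worsens after the first open-label dose.

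**Cost.** SAP and protocol wording plus one derivation flag. The flag works only if severity increases can be identified by date. Protocol 10.1.1 lists a severity grade and start and end dates for each event but does not mention a date of severity change, so this should be confirmed against the AE data first. SAP section 5 says the final CSR covers only VAY736 because the final CFZ533 results were reported in an earlier interim CSR. A SAP edit alone would not reach that cohort; its AE tables would need a check or a rerun.

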Tuberculosis test ⁷	X																		X	
Pregnancy test ⁵	X	X		X	X	X	X	X	X	X	X	X	X	X	X	X	X		X	
Hematology ⁷	X	X		X	X	X	X	X	X	X	X	X	X	X	X	X	X		X	
Clinical Chemistry ⁷	X	X		X	X	X	X	X	X	X	X	X	X	X	X	X	X		X	
CCI																				
Coagulation Panel ⁷	X	X ⁶					X ⁶				X ⁶								X ⁶	
Autoantibodies ⁷	X	X					X				X				X				X	
CCI																				
IMI blood sample ^{7, 16}		X			X					X										
IMI urine sample ^{7, 16}		X			X					X										
CCI																				
Steroid taper ¹¹					X	X	X	X												
PK Cohort 1 ¹²			X	X	X	X	X	X	X	X	X	X	X	X	X	X	X	X	X	
PK Cohort 2 ¹²			X ¹³	X	X ¹³	X	X ¹³	X	X	X	X ¹³	X	X ¹³	X	X ¹³	X	X ¹³		X	
Immunogenicity ^{12, 14}		X		X			X				X	X			X				X	
CCI																				

Epoch	Screening		Treatment																EoT
Visit Name	Screen	Base-line ²	Treatment – blinded period								Treatment – open label period								EoT
Visit Numbers ¹	1	20	110	120	130	140	150	160	170	180	190	200	210	220	230	240	250	260	299
Days	-28 ±2	-1 to 1	1	15 ±2	29 ±2	57 ±2	85 ±2	113 ±2	141 ±2	169 ±3	197 ±3	211 ±2	225 ±3	253 ±3	281 ±3	309 ±3	337 ±4	340 ±1	365 ±5
Weeks	-4	-1 to 1	1	3	5	9	13	17	21	25	29	31	33	37	41	45	49	49	53
Months	-1	-1 to 1	1	1	2	3	4	5	6	7	8	8	9	10	11	12	13	13	14

IRT	X	X ²³		X	X	X	X	X	X	X	X	X	X	X	X	X	X		X
Dose administration ²¹			X ²²	X ⁶	X	X	X	X	X	X	X ²²	X ⁶	X	X	X	X	X		

Adverse Events	As required																		
Concomitant Treatment	As required																		
Comments	As required																		

^X Assessment to be recorded in the clinical database, EoT – End of Treatment

¹ Visit structure given for internal programming purpose only

² Baseline visit may be combined with Visit 110 at Day 1

³ Body Weight, Height (screening only), Temperature, Blood Pressure, Pulse Rate

⁴ Only for Cohort 1 (VAY736); i.v. CS to be applied approximately 1 hour before first dose

⁵ Pregnancy test on Visit 1 (Screening) in serum, all other visits in urine, only females

CCI

⁷ Central Lab

CCI

¹¹ Corticosteroids should be tapered down to 5 mg/day or lower

¹² Samples are collected pre-dose unless otherwise stated

¹³ Cohort 2 (CFZ533): take one PK sample at pre-dose and another sample 90 min AFTER THE START of i.v. infusion

¹⁴ Cohort 1 (VAY736): serum Cohort 2 (CFZ533): plasma

CCI

¹⁶ Only selected sites

CCI

²¹ Dosing must be done after all assessments are completed, except for PK blood sampling in Cohort 2 (CFZ533) at visits V110, 130, 150, 190, 210, 230 and 250 where pre and post dose blood sampling is required

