8.5.2 Immunogenicity

The immunogenicity of multiple i.v. doses of CFZ533 and of multiple s.c. doses of VAY736 will be assessed via the quasi-quantitative analysis of anti-CFZ533 antibodies in plasma, and anti-VAY736 antibodies in serum, respectively.

Blood samples collected for immunogenicity testing will be obtained from all patients and analysis will be performed for CFZ533-, VAY736-, and placebo-treated patients (to assess the rate of pre-existing ADAs). The details of sample processing, handling, storage, shipment and analytical method will be described in a separate laboratory manual.

The SOM is providing operational details including subject numbering, blood log with sample numbers. Further details on sample collection, processing and shipment will be provided in the Central Lab Manual. The detailed methods and analysis will be described in the Bioanalytical Data Report.

The image shows a large, bold, red logo consisting of the letters 'C', 'C', and 'I' in a stylized, sans-serif font. The logo is positioned in the upper left corner of a dark, rectangular area that occupies the bottom half of the page. The background of this area is a solid dark grey or black.

CCI

CCI

9 Study discontinuation and completion

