2. Categorical Analysis of QT/QTc interval data based on the number of subjects meeting or exceeding predefined limits in terms of absolute QT/QTc intervals or changes from baseline will be presented. In addition, a listing of these subjects will be produced by treatment group.

Clinical laboratory evaluations

All laboratory data will be listed by treatment group, subject, and visit and if normal ranges are available abnormalities will be flagged. Summary statistics will be provided by treatment group and visit. Shift tables using the low/normal/high/ (low and high) classification will be used to compare baseline to the worst on-treatment value.

Immunogenicity

All immunogenicity results will be listed by treatment group, subject and visit/time. Anti-VAY736 antibody and anti-CFZ533 antibody results will be listed by treatment group, subject and visit. The proportion of ADA-positive patients will be listed by treatment group and visit.

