1.3 Study objectives

Table 1-1 Objectives and related endpoints

Objective(s)	Endpoint(s)
Primary objective(s)	Endpoint(s) for primary objective(s)

To determine the effect of VAY736 and of CFZ533 versus their respective placebo on disease activity in SLE patients at Week 29 compared to baseline	
SRI-4 response status at Week 29 with reduced steroid dose maintained between Weeks 17 and 29
Secondary objective(s)	Endpoint(s) for secondary objective(s)

To assess safety and tolerability of VAY736 and of CFZ533 in patients with SLE	
Adverse events and other safety data such as vital signs, ECG and laboratory results recorded during study

To determine the change from baseline in the Physicians' Global Assessment (PhGA) at Week 29 in VAY736-, CFZ533- or their respective placebo-treated arms	
Changes between baseline and Week 29 in the PhGA visual analog scale (VAS) assessing patient's overall disease activity

To determine the change from baseline in the Patient's Global Assessment (PGA) at Week 29 in VAY736, CFZ533 or their respective placebo-treated arms	
Changes between baseline and Week 29 in the patients' VAS assessing their global disease activity

To determine the pharmacokinetics (PK) of multiple doses of VAY736 (s.c.) and CFZ533 (i.v.) in SLE patients	
PK Cohort 1 (VAY736): free VAY736 serum concentration (C_{trough}). PK Cohort 2 (CFZ533): free CFZ533 concentration in plasma (C_{max}, C_{trough}).

To assess the effect of VAY736 and of CFZ533 versus their respective placebo to prevent disease flares in SLE patients	
Flare rate and time to first flare, with flare defined as one new 'A' score or two or more 'B' score using BILAG -2004

Objective(s)	Endpoint(s)

To evaluate the immunogenicity of multiple doses of VAY736 (s.c.) or CFZ533 (i.v.) in SLE patients	
Anti-VAY736 (Cohort 1) or anti-CFZ533 (Cohort 2) antibodies and incidence of ADA-positive patients.

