Pregnancy test results will be listed by treatment, patient and visit/time.

[figure not shown]
Immunogenicity

[figure not shown]
The frequency and proportion of ADA-positive patients will be displayed by treatment and visit. Immunogenicity results will be listed by treatment, patient and visit/time.

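### The plan names ADA incidence as a secondary endpoint but tabulates only the proportion positive at each visit, which does not determine a per-patient or new-onset incidence

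*SAP*

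**What the plan says.** Protocol Table 2-1 and SAP Table 1-1 word the secondary endpoint the same way: "Anti-VAY736 (Cohort 1) or anti-CFZ533 (Cohort 2) antibodies and incidence of ADA-positive patients".

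For the analysis, SAP 8.2 (Immunogenicity) plans two outputs:

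- a table: "The frequency and proportion of ADA-positive patients will be displayed by treatment and visit";
- a listing: "Immunogenicity results will be listed by treatment, patient and visit/time".

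Protocol 12.5.2 matches this: "The proportion of ADA-positive patients will be listed by treatment group and visit".

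Protocol 8.5.2 has samples assayed in active and placebo patients alike, "to assess the rate of pre-existing ADAs", so the plan expects some positivity before exposure. Samples fall at Baseline and Weeks 3, 13, 29, 31, 41 and 53 (Protocol Table 8-1), then at Weeks 61 and 69 and at the end-of-study visit (Table 8-2). Footnote 12 to Table 8-1 applies to them: "Samples are collected pre-dose unless otherwise stated". Placebo patients receive their first active dose at the end of the Week 29 visit (Protocol section 3; SAP 1.4).

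No readable text defines an ever-positive patient, newly arising ADA, a denominator for incidence, or the reference sample for patients who switch from placebo.

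**The concern.** Incidence counts patients who become positive over a stretch of follow-up. A proportion at a visit counts patients who are positive on that day. The two can differ in either direction. If positivity is transient, each visit shows only a fraction of the patients who were ever positive. If positivity was there before treatment and persists, each visit shows positives although none is new.

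The SAP makes this within-patient link for other safety data. Laboratory results are cross-tabulated as baseline against worst later value. Adverse events have a treatment-emergent definition, and a patient counts once per body system. ADA, a named secondary endpoint, gets neither.

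At stake is whether the report can state a single ADA incidence for each drug that separates antibodies present before active drug from those that are new.

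**Working it through.** The plan gives no target figure for ADA incidence, so there is nothing to reproduce. The check asks how much the planned table pins down.

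**Inputs**

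- n = 30 per arm (Protocol 12.8.1).
- V, the number of samples after the reference (Protocol Tables 8-1 and 8-2):
  - 3 in the blinded period (Weeks 3, 13, 29);
  - 8 through Week 69 (adding Weeks 31, 41, 53, 61, 69);
  - 5 through Week 69 for placebo patients counted from Week 29.
- b, the number positive at the reference sample, and m, the number positive at each later sample. Both are assumed.

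**Bounds given only the by-visit counts**

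- Ever positive after reference: from m (always the same patients) to min(n, m × V) (different patients each time).
- Newly positive among those negative at reference: from max(0, m − b) to min(n − b, m × V).

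**Results**

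| Assumed counts | V | Ever positive after reference | Newly positive among reference-negatives |
|---|---|---|---|
| b = 3, m = 3 | 3 | 3 to 9 of 30 (10% to 30%) | 0 to 9 of 27 (0% to 33%) |
| b = 3, m = 3 | 8 | 3 to 24 of 30 (10% to 80%) | 0 to 24 of 27 (0% to 89%) |
| b = 1, m = 1 | 3 | 1 to 3 of 30 (3% to 10%) | 0 to 3 of 29 (0% to 10%) |

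For placebo patients after the switch, with 3 of 30 positive at Week 29 and at each of 5 later samples, the upper bound is min(27, 3 × 5) = 15 of 27 (56%) and the lower bound is 0. Within each case, every value in the range produces an identical by-visit table.

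**How likely is the ambiguity to matter?** Protocol 4.5 reports 2 positive cases among about 435 subjects treated with CFZ533.

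- Rate: 2 / 435 = 0.46%.
- Expected positives in an arm of 30: 30 × 2/435 = 0.14.
- Chance of none: (433/435)^30 = 0.87.

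With no positives at any visit, the by-visit table gives the incidence exactly: zero. The assumed 3 of 30 is therefore far above the one documented rate. That rate comes from CFZ533 only, in healthy volunteers and patients with other conditions; no VAY736 rate is readable.

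**The case against.** The strongest reply is that nothing is lost. The listing shows every result for every patient, and with about 30 patients per arm a reader can count who turned positive and when. The antibody results are themselves part of the endpoint, and the listing covers them. Protocol and SAP agree with each other, the study is non-confirmatory, and no decision rule depends on ADA. A derivation could also sit in the programming specifications or table shells that SAP 1.1 mentions, in the bioanalytical report, or in redacted SAP text.

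Much of this stands. The data exist, and the matter is small. But a listing is not a summary: two people counting from it could differ on the reference sample, the denominator, or how to treat patients who switch. Protocol 12.5.2, which is readable, also stops at the by-visit proportion.

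A reader might infer three stronger things that the documents do not support:

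- That the immunogenicity objective cannot be answered. It can, from the listing.
- That the switchers' Week 29 reference is absent. It is not: Week 29 is a scheduled pre-dose sample, so its proportion appears in the table. Only the link to later results within a patient is missing.
- That incidence will be badly misstated. That needs ADA to be fairly common, and at the documented CFZ533 rate it would not be.

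**Conclusion.** The planned table does not measure the incidence that the endpoint names, and it cannot show whether positivity after the start of active drug is new. That is a matter of logic and does not depend on the assumed rates. The size does: with 3 of 30 positive throughout, new positivity by Week 29 could be 0% or 33% of baseline-negative patients under one and the same table; at the CFZ533 rate in Protocol 4.5, most arms would have no positives and the gap would vanish. For VAY736 the size is unknown from the readable text. The conclusion assumes that no definition sits in redacted or separate documents. It is a minor point about a descriptive secondary endpoint, worth fixing because the fix is cheap.

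**What to change.** Keep the by-visit table and the listing. Add to SAP 8.2 one per-patient table by cohort and treatment sequence, giving:

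- (a) patients positive at reference;
- (b) patients newly positive at any later sample, among those negative at reference;
- (c) patients ever positive after reference.

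State each denominator, including how patients without a reference or any later result are counted.

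Reference samples: the baseline-visit pre-dose sample for patients randomised to active drug, and for the placebo arm in the blinded period; the Week 29 pre-dose sample for placebo patients after they switch. Because SAP section 8 places Week 29 in the open-label period for all safety analyses, add a line saying that for this table the Week 29 pre-dose sample closes the blinded period.

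Report boosted ADA (a rise in patients already positive) only if a level rule is pre-specified; Protocol 8.5.2 describes the assay as quasi-quantitative, and no such rule is readable.

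SAP section 5 says that the CFZ533 final results are already reported and that the final report covers VAY736 only. The table therefore goes directly into the VAY736 report; for Cohort 2, label it supplementary.

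Cost: one derived patient-level status and one table from data already collected. No new samples are needed, and the primary analysis is untouched.
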